7.2 Data analysis

Data analysis will be guided by a statistical analysis plan, which will be developed before the database is locked. Data analysis will be undertaken at the George Institute for Global Health by statisticians using SAS software. To address the primary objectives descriptive statistics will be used including univariate comparisons. Only sites participating in both SAFE TRIPS and FLUID TRIPS will be included in the comparison of fluid use over time. To address the secondary objective – a multivariate analysis will be completed adjusting for predictors of fluid choice. An example of the proposed analysis can be found in the SAFE TRIPS publication³.

8 Data Management

The data management and analysis will be undertaken by the George Institute for Global Health. The principal means of data collection and data processing will be via online data entry performed by the research coordinators at each site.

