4.1 Primary objectives

- 1. To describe the amount and type of resuscitation fluid currently administered to adult patients in intensive care units (ICU) in different countries
- 2. To compare the types of fluids used for resuscitation collected in this survey to data collected in the international survey conducted by our group in the 2007 Saline versus Albumin Fluid Evaluation Translating Research Into Practice Study.³

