4.2 Secondary objectives

- 1. To describe and compare the costs of fluid choice between different geographical regions
- 2. To develop policy recommendations for practice guidelines

5 Study Design - Cross Sectional Survey

The study is based on the methodological design of SAFE-TRIPS. An international cross-sectional survey will be undertaken which audits fluid resuscitation practice in participating

adult ICUs on a single day, commencing at the beginning of the relevant chart day and including all patients in the ICU and admitted during the 24-hour study period. The cross-sectional survey will address both primary objectives.

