5.4.2 Individual patient data

Patients who receive fluid resuscitation will have the following data collected:

Baseline data

- Sex
- Age
- ICU admission date
- Admission source and type
- Diagnosis
- Weight

- Diagnostic subcategories and details (trauma/sepsis/ARDS)
- GCS
- Cranial CT scan performed
- Abnormality on cranial CT
- Severity of disease score

Fluid Resuscitation Episode Data

- Time of resuscitation episodes
- Indications
- Prescriber characteristics
- SOFA score respiratory and cardiovascular only
- Renal replacement therapy
- Mechanical ventilation
- Non-invasive ventilation
- ECMO
- ICP monitor
- ICP value
- Heart rate
- MAP
- Systolic and diastolic ABP
- CVP
- PCWP
- Lab results (creatinine, bilirubin, base excess or deficit, lactate, serum albumin)
- Urine and fluid output previous complete hour
- Crystalloid type and volume
- Colloid type and volume
- Fluid resuscitation infusion totals for the study day
- Total daily fluid balance input and output volumes

6 Safety Monitoring

As this is a cross-sectional study using data collected as part of routine clinical practice, no safety monitoring will be undertaken.

7 Statistical Analysis Plan

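### Section 7.2 assigns univariate comparisons to the 2007-to-2014 comparison and case-mix adjustment to another objective, so a shift in patient mix could be mistaken for part of a change in practice

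*Protocol*

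**What the plan says.** Section 4.1 makes the comparison with 2007 the second primary objective: "To compare the types of fluids used for resuscitation collected in this survey to data collected in the international survey" of 2007. Section 7.2 then assigns methods by objective. For the primary objectives: "To address the primary objectives descriptive statistics will be used including univariate comparisons". For the rest: "To address the secondary objective – a multivariate analysis will be completed adjusting for predictors of fluid choice".

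Section 4.2 lists two secondary objectives. One is "To describe and compare the costs of fluid choice between different geographical regions"; the other is the development of policy recommendations. Neither is the comparison over time.

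The one comparability measure that section 7.2 names for the time comparison is restriction by site: "Only sites participating in both SAFE TRIPS and FLUID TRIPS will be included in the comparison of fluid use over time".

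Section 5.4.2 collects age, admission source and type, diagnosis with trauma and sepsis detail, and a severity score. On the earlier survey, section 5 says: "The study is based on the methodological design of SAFE-TRIPS". Section 3.2 states the purpose: to find out whether fluid resuscitation patterns have been influenced by the reviews and trials published since 2007.

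**The concern.** Matching on site removes differences between ICUs. It leaves differences between the patients those ICUs held on two survey days about seven years apart. Section 7.1 expects only 5 to 10 patients per ICU, and section 5.4 collects data only on patients who received fluid resuscitation. If the same units treated, say, more sepsis and fewer surgical patients in 2014, and those groups tend to receive different fluids, the crude proportions move even though prescribing within each group has not changed.

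At stake is the interpretation that section 3.2 wants to draw. A crude difference describes what was given. It cannot by itself separate changed prescribing from changed patients, although the survey collects variables that could help to do so.

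**Working it through.** **Inputs from section 7.1:** 350 ICUs, 5 to 10 patients each, ICC 0.12, baseline prevalence 50%, 90% power for a 6-point change. **Assumed:** two-sided 5% test (section 7.1 states no alpha); two independent surveys of equal size; 7.5 patients per ICU, which is the midpoint and also 2100/280.

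**Step 1: the plan's own figure.**
- Design effect = 1 + (7.5 − 1) × 0.12 = 1.78.
- Patients per survey = 350 × 7.5 = 2625; effective number = 2625/1.78 = 1475.
- SE of the difference = √(2 × 0.25/1475) = 1.84 points.
- Power for 6 points ≈ Φ(6/1.84 − 1.96) = Φ(1.30) = 90%.

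The stated 90% is reproduced. It is about 83% at 5 patients per ICU and 94% at 10. The figure is that of an unadjusted two-proportion comparison inflated for clustering, which fits the univariate method in section 7.2. It is not in dispute.

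**Step 2: size of a spurious change.** With no change of practice within any patient group,

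spurious change = (shift in a group's share) × (difference in fluid use between groups).

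The documents give neither quantity, so both are assumed:

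| Shift in mix | Difference 10 points | 20 points | 30 points |
|---|---|---|---|
| 10 points | 1.0 | 2.0 | 3.0 |
| 15 points | 1.5 | 3.0 | 4.5 |
| 20 points | 2.0 | 4.0 | 6.0 |

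**Step 3: how often it would be called significant.** For a spurious change b, the probability is 1 − Φ(1.96 − b/SE) + Φ(−1.96 − b/SE).

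With 350 independent ICUs per survey (SE 1.84 points):
- b = 1.5: 13%
- b = 3: 37%
- b = 4.5: 69%
- b = 6: 90%

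The planned comparison uses only ICUs in both surveys, and the protocol does not give their number. With an assumed 100:
- Effective number = 100 × 7.5/1.78 = 421.
- SE = √(0.5/421) = 3.4 points.
- For b = 3, the probability is 14%.

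Fewer matched ICUs make a false declaration less likely but leave the bias as large as before. Both calculations treat the two surveys as independent, which matched ICUs are not, so they are illustrations rather than properties of the planned test.

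**The case against.** **The text is not exclusive.** A reader might infer that the 2007 comparison will be univariate and nothing else. Section 7.2 does not say that: its wording includes univariate comparisons without ruling out others, and it defers to a statistical analysis plan and points to the SAFE-TRIPS publication as an example. Neither is at hand, and an adjusted analysis may appear there. What stands against the protocol is narrower. It assigns methods by objective, and adjustment goes to an objective that is not the time comparison.

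**The crude difference is the right quantity for a descriptive trend.** Objective 2 asks for a comparison of fluid types, and the unadjusted difference answers it. This stands. A reader might infer that an adjusted estimate should replace the crude one as the main result; the documents do not support that. The case for adjustment comes from the interpretation in section 3.2, and it supports an added estimate.

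**Patient mix is not the only remaining difference.** In section 3.1 the 2007 definition of fluid resuscitation covers a bolus of crystalloid, colloid or blood product given within an hour. Section 5.4 lists no blood product and adds crystalloid infusions of at least 5 mL/kg/hour and any colloid infusion. This changes which episodes count, and case-mix adjustment cannot repair it. It would therefore be wrong to call patient mix the main difference left after matching.

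**Patient factors may matter little.** Section 3.1 reports that in 2007 location, rather than patient factors, appeared to be a strong determinant of variation. That points to the lower end of the range. It does not settle the matter, because location is held fixed once the sites are matched.

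**Some candidate covariates are unsafe.** Section 3.1 reports trials in which starch increased renal replacement therapy. RRT recorded at the episode may follow from earlier fluid choice, and adjusting for it could remove or distort part of a real change. This stands, and RRT should be left out.

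**Conclusion.** The point holds in a limited form. Section 7.2 assigns univariate comparisons to the 2007-to-2014 comparison, places adjustment elsewhere, and relies on site restriction for comparability, while section 3.2 means to read the result as an influence of evidence on practice. A shift in patient mix could therefore be mistaken for part of a change in practice.

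That consequence is conditional. It needs both a shift in mix and a difference in fluid use between patient groups, and the documents give the size of neither. The 1-to-6-point range rests wholly on assumed inputs. If mix was stable, or only weakly related to fluid choice, the crude and adjusted figures will agree. A reader should not infer that the survey will report a false change, or that the significance probabilities above describe the matched-site comparison.

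**What to change.** In section 7.2, keep the crude 2007-to-2014 difference for each main fluid type as the descriptive result and add an adjusted difference beside it. The adjusted figure should come from a model with a survey-year term that accounts for clustering by ICU; a standardised risk difference from a logistic model is one option. Covariates should be patient variables recorded alike in both surveys and not plausibly caused by earlier fluid choice: for example age, admission source and type, diagnosis group including trauma and sepsis, and severity score, but not RRT. State that any conclusion about changed practice will rest on both estimates.

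The cost is a sentence or two in the protocol or analysis plan and one further model, with no new data collection. There are three limits. Only variables coded alike in 2007 and 2014 can be used, and the protocol does not list those of 2007. Missing covariates need a handling rule. The changed definition of fluid resuscitation needs separate treatment, because adjustment leaves it untouched.

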5.1 Sampling

Convenience sampling will be used leveraging from the previous collaborators in SAFE-TRIPS (391 centres from 25 countries). Additionally, sampling will be sought through established ICU clinical trials networks.

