7.1 Sample size and power

Due to the uncertain nature of observational research, no specific sample size has been calculated for this study. Based on the experience of SAFE TRIPS we anticipate recruiting a similar sample size (n>5000 patients; n>350 sites). A sample size of 280 ICUs and 2100 patients will allow us to estimate the overall prevalence of each fluid type very precisely with 95% confidence intervals that will be no wider than 6 percentage points. Furthermore,

we will be able to suitably estimate country specific prevalence rates with a precision of around 20 percentage points. Additionally, by recruiting between 5 and 10 patients from 350 ICUs, we will have 90% power to detect absolute changes in fluid prevalence over time of 6 percentage points.

All calculations assume a baseline prevalence of 50% which leads to the lowest precision (compared to lower prevalence assumptions); it is therefore likely that actual confidence intervals and detectable changes will be even smaller. These estimates also take into account the correlation of patients within ICUs. Based on the SAFE-TRIPS data, we have estimated that the Intraclass Coefficient (ICC) for fluid use is approximately 12%. Sample size calculations were performed using PASS 2008 and procedures appropriate for cluster-randomised studies.²⁵

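### The 90% power for a 6-point change over time is stated for 350 ICUs, but only ICUs in both surveys enter that comparison, and their expected number is not given

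*Protocol*

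**What the plan says.** Primary objective 2 (protocol section 4.1) is to compare the types of resuscitation fluid used now with those recorded in the 2007 SAFE-TRIPS survey. Three sections bear on how precisely this can be done.

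- **Section 7.1** gives the only power statement for this comparison: "we will have 90% power to detect absolute changes in fluid prevalence over time of 6 percentage points". The recruitment on which it rests is put this way: "by recruiting between 5 and 10 patients from 350 ICUs". Its inputs are a prevalence ("All calculations assume a baseline prevalence of 50" percent) and an intracluster correlation ("we have estimated that the Intraclass Coefficient (ICC) for fluid use is approximately 12" percent). On method: "Sample size calculations were performed using PASS 2008 and procedures appropriate for cluster-randomised studies". The section also expects more than 350 sites in total, without dividing them into returning and new sites.
- **Section 7.2** defines the analysis set: "Only sites participating in both SAFE TRIPS and FLUID TRIPS will be included in the comparison of fluid use over time". The analysis for the primary objectives is descriptive, with univariate comparisons.
- **Section 5.1** names two sources of sites. One is the former SAFE-TRIPS collaborators, 391 centres in 25 countries. The other is wider: "Additionally, sampling will be sought through established ICU clinical trials networks".

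The protocol gives no expected number of returning centres, no between-period correlation within an ICU, and no alpha or sidedness for the power figure.

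**The concern.** The number that determines power for the over-time comparison is the number of ICUs common to both surveys. Section 7.1 quotes power for 350 ICUs without saying that these must all be returning centres. A network site that was not in SAFE-TRIPS counts towards the Fluid-TRIPS total but adds nothing to this comparison. If the 350 is simply the recruitment target, the stated power belongs to a larger set of ICUs than the one to be analysed.

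The figure supports a primary objective. Section 7.1 adds that the detectable changes will probably be smaller still, on the ground that 50% is the worst-case prevalence. With fewer common ICUs they could instead be larger, and a reader who relied on the stated figure could take an unremarkable result as evidence against a 6-point shift.

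**Working it through.** **Inputs.** From section 7.1: prevalence 50%, ICC 0.12, 350 ICUs, m = 5 to 10 patients per ICU. The midpoint is 7.5, which is also the mean implied by the precision statement ("A sample size of 280 ICUs and 2100 patients": 2100/280 = 7.5). From section 5.1: at most 391 returning centres. Assumed: two-sided alpha 0.05, in line with the 95% intervals in the same section, and the between-period correlation r, for which the protocol gives no value.

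**Formula.** For k ICUs in each period,

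Var(difference) = [2 × 0.25/(k m)] × D, with D = 1 + (m − 1) × 0.12 − m × 0.12 × r.

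Setting r = 0 treats the two periods as independent sets of clusters, as a parallel cluster-randomised formula does. Detectable change at 90% power = (1.960 + 1.282) × √Var.

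**Step 1: reproduce the plan's figure.** With m = 7.5 and r = 0, D = 1 + 6.5 × 0.12 = 1.78.

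- k = 350 per period: √(0.5 × 1.78/2625) = 0.01841. The detectable change is 5.97 points, and power for 6 points is 90.3%. This matches the stated figure.
- 350 in total (175 per period): power is 63%. This does not match.
- Cross-check on the neighbouring claim for 280 ICUs and 2100 patients: the interval width is 2 × 1.96 × √(0.25 × 1.78/2100) = 5.7 points, against a stated maximum of 6.

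**Step 2: common ICUs needed by the same method.** k = (1.960 + 1.282)² × 0.5/0.06² × D/m = 1459.4 × D/m.

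| Patients per ICU | D (r = 0) | Common ICUs needed | Share of 391 |
|---|---|---|---|
| 5 | 1.48 | 432 | more than exist |
| 7.5 | 1.78 | 346 | 89% |
| 10 | 2.08 | 304 | 78% |

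**Step 3: power if fewer centres return (m = 7.5, r = 0).** The numbers returning are assumptions.

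| Common ICUs | Power for 6 points | Detectable change at 90% power |
|---|---|---|
| 300 | 85.5% | 6.4 points |
| 200 | 69% | 7.9 points |
| 100 | 41% | 11.2 points |

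**Step 4: allow for matching (r assumed).**

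- m = 7.5, r = 0.5: D = 1.33, k ≈ 259 (66% of 391).
- m = 7.5, r = 0.8: D = 1.06, k ≈ 207 (53%).
- m = 10, r = 0.8: D = 1.12, k ≈ 164 (42%).

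**Step 5: prevalence below 50%.** For an illustrative change from 20% to 26% (assumed), replace 2 × 0.25 by 0.20 × 0.80 + 0.26 × 0.74 = 0.3524. With m = 7.5 and r = 0.5, k ≈ 183 (47%).

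**The case against.** The case for leaving section 7.1 alone has several strands, and parts of it stand.

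- **The sentence is conditional and may already mean returning centres.** 350 is below 391, and section 3.2 says the study builds on the SAFE-TRIPS infrastructure. The document does not exclude this reading. A reader might infer that some of the 350 are bound to be new sites, but no split is given, so that is only an inference. Even on the favourable reading, the figure rests on about 90% of centres returning (350/391), which is nowhere stated.
- **The reconstruction is not unique.** Alpha and sidedness are unstated. One-sided testing with 5 patients per ICU gives about 90%. So does a two-sided test with 5 patients and 350 matched ICUs at a between-period correlation near 0.46. The independent-period, two-sided reading fits the named cluster-randomised procedures best, but it cannot be called the only one. The matched alternative still needs 350 common ICUs.
- **Ignoring the matching is conservative.** With positive correlation a matched analysis does better than the formula. This stands, so the omission is not a further defect that lowers power. The protocol does not claim the gain, however.
- **50% is the worst-case prevalence, and 7.5 is only a midpoint.** This also stands. A general claim that most SAFE-TRIPS centres must return fails in the favourable cases of steps 4 and 5.
- **The study is a descriptive audit for which no specific sample size was calculated.** True, and the eventual confidence interval will show the precision achieved. The section nonetheless makes a definite 90% and 6-point claim for a primary objective, and that claim should refer to the set to be analysed.

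**Conclusion.** The point holds as a mismatch between a power statement and its analysis set. By the protocol's own method, the 90% for 6 points requires about 346 ICUs common to both surveys at 7.5 patients per ICU, 89% of the SAFE-TRIPS centres. The number expected is not stated. With 200 common ICUs, power would be about 69% and the detectable change 7.9 points.

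Two stronger conclusions are tempting and not supported. The arithmetic is not wrong: it reproduces. Nor do the documents show the comparison to be underpowered, because the return rate and the between-period correlation are both unknown, and favourable values bring the need below half of the centres. The direction of the loss with fewer common ICUs is certain; its size rests on two-sided alpha 0.05, the assumed number returning and the assumed correlation.

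Severity is moderate. Restricting the comparison to common sites is sound protection against a change in site mix and should stay.

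**What to change.** In section 7.1, replace the 90% and 6-point sentence with a short table of the change detectable at 90% power by number of ICUs common to both surveys (for example 100, 200 and 300), for 5 to 10 patients per ICU. State alpha and sidedness, and give an explicit between-period correlation, with 0 as the conservative case. State the expected number of returning centres if one is available.

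Keep the common-site comparison in section 7.2 as primary. A supportive mixed model using all sites from both surveys is optional and can be left to the SAP.

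The cost is a few lines of text and a recalculation. No extra sites or data are needed. The downside is that the stated sensitivity may look less favourable than it does now.

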8.1 Site monitoring

No site monitoring will be performed.

8.2 Data recording and document retention

Each participating site will enter de-identified data into an electronic CRF (eCRF) using REDCap, a secure online data capture system developed by Vanderbilt University and hosted at the George Institute. Each site will access the system through an individual password protected account, and will only have access to site-specific data.

All data sent to the George Institute will be de-identified. Master log sheets with identifying details will remain confidential and will be stored securely at participating sites to enable data queries to be addressed if required. Master log sheets or any other identifying information will not be submitted to the study office at the George Institute.

All data collected by the study will be kept for a minimum of 7 years, or as otherwise required by regulatory authorities. The George Institute will be the data custodian and all

electronic data will be stored and backed up on password-protected databases. All paper data will be archived and stored in a secure facility.

8.3 Data quality assurance

Data entered by each site will be password-protected and the ability to access or change data prior to locking of the database will be restricted to that site and staff managing data at the George Institute. Once initial data collection has been completed, missing data and implausible values will be identified using predetermined objective criteria, and queries resolved through direct communication with sites if required. The Fluid-TRIPS management committee will oversee this data cleaning process. Treatment of outliers and missing data will be in accordance with the statistical analysis plan.

9 Funding

The George Institute will fund data management, operations and analysis. No site payments are available at the time of writing but funding is currently being sought. A participating centre Memorandum of Understanding (MOU) will be signed if required between the participating sites and the George Institute for Global Health.

10 Project Timeline

Anticipated timelines:

Date	Project Milestone
September 2013	Invite expressions of interest from international collaborators
October 2013	Identify site and country coordinators and make initial contact
November 2013	Managment committee finalise protocol & CRF
December 2013	Comments from international liaison committee on protocol and
	CRF
January 2014	Finalise protocol and CRF. Submit low & negligible risk ethics
	application to lead HREC in NSW
January 2014	Finalise participating countries/sites and distribute study
	documents
February 2014	Submit low & negligible risk ethics applications to Australian and
	international HRECs where appropriate
30 th April 2014	Data collection day 1
21 st May 2014	Data collection day 2
11 th June 2014	Data collection day 3
16 th July 2014	Data collection day 4
20 th August 2014	Data collection day 5
17 th September 2014	Data collection day 6
15 th October 2014	Data collection day 7
November 2014	Finalise data collection
February 2015	All data entered and queries resolved

March 2015	Data analysis
June 2015	Final manuscript(s) submitted for publication

11 Participating Sites

